#### **9.5.6.6 Week 9**

- Obtain predose blood samples for hematology and chemistry (including thyroid, glucose, but not HbA1c) analysis (see [Section 9.5.4.6](#) for details concerning test results and study participation).
- Collect predose urine sample for urinalysis and also for a pregnancy test for females of childbearing potential; the pregnancy test must be negative for the subject to receive study drug.
- Collect predose blood samples for immunogenicity and PK testing.
- Enquire about signs and symptoms and concomitant medications throughout the visit.
- Collect predose vital signs. Additional vital sign monitoring may be performed in the event of infusion-associated AEs (see [Section 9.5.4.3](#) for details).
- Obtain study medication vial assignment and volume of study drug to be administered from EDC.
- Administer study drug and record date, volume and rate of infusion, and start/stop times of dosing.
- Collect blood samples for PK analyses at the end of the infusion.

Subjects will be discharged from the study center after all of the procedures have been completed and instructed to return for a clinic visit at Week 12.

#### **9.5.6.7 Week 12**

- Obtain predose blood samples for hematology and chemistry (including thyroid, glucose, and HbA1c) analysis (see [Section 9.5.4.6](#) for details concerning test results and study participation).

- Collect predose urine sample for urinalysis and also for a pregnancy test for females of childbearing potential; the pregnancy test must be negative for the subject to receive study drug.
- Enquire about signs and symptoms and concomitant medications throughout the visit.
- Perform predose 12-lead ECG.
- Perform predose physical and ophthalmic examinations, including vital signs. Additional vital sign monitoring may be performed in the event of infusion-associated AEs (see [Section 9.5.4.3](#) for details).
- Measure weight.
- Perform predose efficacy assessments (CAS, Clinical Measures of Severity including proptosis, diplopia and motility restriction).
- Administer predose GO-QoL questionnaire.
- Obtain study medication vial assignment and volume of study drug to be administered from EDC.
- Administer study drug and record date, volume and rate of infusion, and start/stop times of dosing.

Subjects will be discharged from the study center after all of the procedures have been completed and will be instructed to return to the clinic at Week 15.

#### **9.5.6.8 Week 15**

- Obtain predose blood samples for hematology and glucose analysis (see [Section 9.5.4.6](#) for details concerning test results and study participation).
- Perform predose urine pregnancy test for females of childbearing potential; the pregnancy test must be negative for the subject to receive study drug.
- Enquire about signs and symptoms and concomitant medications throughout the visit.
- Collect predose vital signs. Additional vital sign monitoring may be performed in the event of infusion-associated AEs (see [Section 9.5.4.3](#) for details).
- Obtain study medication vial assignment and volume of study drug to be administered from EDC.
- Administer study drug and record date, volume and rate of infusion, and start/stop times of dosing.

Subjects will be discharged from the study center after all of the procedures have been completed and will be instructed to return to the clinic at Week 18.

#### **9.5.6.9 Week 18**

- Obtain predose blood samples for hematology and chemistry (including thyroid, glucose, but not HbA1c) analysis (see [Section 9.5.4.6](#) for details concerning test results and study participation).
- Collect predose urine sample for urinalysis and also for a pregnancy test for females of childbearing potential; the pregnancy test must be negative for the subject to receive study drug.
- Enquire about signs and symptoms and concomitant medications throughout the visit.
- Perform predose physical and ophthalmic examinations, including vital signs. Additional vital sign monitoring may be performed in the event of infusion-associated AEs (see [Section 9.5.4.3](#) for details).
- Perform predose efficacy assessments (CAS, Clinical Measures of Severity including proptosis, diplopia and motility restriction).
- Obtain study medication vial assignment and volume of study drug to be administered from EDC.
- Administer study drug and record date, volume and rate of infusion, and start/stop times of dosing.

Subjects will be discharged from the study center after all of the procedures have been completed and will be instructed to return to the clinic at Week 21.

#### **9.5.6.10 Week 21**

- Obtain predose blood samples for hematology and glucose analysis (see [Section 9.5.4.6](#) for details concerning test results and study participation).
- Collect predose urine sample for a pregnancy test for females of childbearing potential. The pregnancy test must be negative for those subjects to receive study drug.
- Enquire about signs and symptoms and concomitant medications throughout the visit.
- Collect predose vital signs. Additional vital sign monitoring may be performed in the event of infusion-associated AEs (see [Section 9.5.4.3](#) for details).
- Obtain study medication vial assignment and volume of study drug to be administered from EDC.

- Administer study drug and record date, volume and rate of infusion, and start/stop times of dosing.

Subjects will be discharged from the study center after all of the procedures have been completed and will be instructed to return to the clinic at Week 24.

#### **9.5.6.11 Week 24/Premature Withdrawal – Treatment Period**

Week 24 is the final visit of the Treatment Period. Study drug is not administered.

- Obtain blood samples for hematology and chemistry (including thyroid, glucose, and HbA1c) analysis (see [Section 9.5.4.6](#) for details concerning test results and study participation).
- Collect urine sample for urinalysis and also for a pregnancy test for females of childbearing potential.
- Collect blood sample for immunogenicity testing (only subjects who complete the Treatment Period, not those who prematurely discontinue study drug administration).
- Collect blood sample for PK analyses (only subjects who complete the Treatment Period, not those who prematurely discontinue study drug administration).
- Enquire about signs and symptoms and concomitant medications throughout the visit.
- Perform 12-lead ECG.
- Perform physical and ophthalmic examinations, including vital signs.
- Measure weight.
- Perform efficacy assessments (CAS, Clinical Measures of Severity including proptosis, diplopia and motility restriction).
- Administer GO-QoL questionnaire.

Subjects who were proptosis non-responders in Study HZNP-TEP-301 will enter the Follow-Up Period and will be instructed to return to the clinic in one month for the first follow-up visit. Subjects who relapsed during the Follow-Up Period of HZNP-TEP-301 and chose to enter this extension study will not participate in the Follow-Up Period.

#### **9.5.6.12 Month 7 – Follow-Up Period**

- Collect urine sample for a pregnancy test for females of childbearing potential.
- Enquire about signs and symptoms and concomitant medications throughout the visit.

- Collect vital signs.
- Perform efficacy assessments (CAS, Clinical Measures of Severity including proptosis, diplopia and motility restriction).
- Administer GO-QoL questionnaire.

Subjects will be discharged from the study center after all of the procedures have been completed and will be instructed to return to the clinic for the Month 9 Follow-Up Visit.

#### **9.5.6.13 Month 9 – Follow-Up Period**

- Obtain blood samples for hematology and chemistry (including thyroid, glucose, and HbA1c) analysis.
- Collect urine sample for urinalysis and also for a pregnancy test for females of childbearing potential.
- Enquire about signs and symptoms and concomitant medications throughout the visit.
- Collect blood sample for immunogenicity testing.
- Collect vital signs.
- Perform efficacy assessments (CAS, Clinical Measures of Severity including proptosis, diplopia and motility restriction).
- Measure weight.

Subjects will be discharged from the study center after all of the procedures have been completed and will be instructed to return to the clinic at Month 12.

#### **9.5.6.14 Month 12**

##### **9.5.6.14.1 Month 12/Premature Withdrawal – Follow-Up Period for Proptosis Non-responders in Study HZNP-TEP-301**

- Obtain blood samples for hematology and chemistry (including thyroid, glucose, and HbA1c) analysis.
- Collect urine sample for urinalysis.
- Collect urine sample for a pregnancy test for females of childbearing potential if the subject discontinued from the study prior to Month 9 of the Follow-Up Period.
- Collect blood sample for immunogenicity testing.

- Enquire about signs and symptoms and concomitant medications throughout the visit.
- Perform 12-lead ECG.
- Perform physical and ophthalmic examinations, including vital signs.
- Measure weight.
- Perform efficacy assessments (CAS, Clinical Measures of Severity including proptosis, diplopia and motility restriction).
- Administer GO-QoL questionnaire.

Subjects will be discharged from the study center after all of the procedures have been completed.

#### **9.5.6.14.2 Month 12 – Follow-Up Contact for Subjects Who Relapsed in Study HZNP-TEP-301**

Subjects who complete the Week 24 Visit will be contacted 6 months later via phone or email by research staff to enquire if any treatment for TED has been received since last study contact. If yes, subject will be questioned regarding type of treatment and outcome/response.

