TED01RV was the first study in which non-oncology subjects received teprotumumab. This study enrolled 87 subjects (43 teprotumumab; 44 placebo) between the ages of 18 and 75 years with recent onset ( $\leq$  9 months from diagnosis) moderate-to-severe active TED. The primary efficacy endpoint was the overall responder rate (decreases from Baseline of  $\geq$  2 points in overall Clinical Activity Score [CAS] and  $\geq$  2 mm in proptosis, provided that there was no deterioration [i.e., increases of  $\geq$  2 points in CAS or  $\geq$  2 mm in proptosis] in the non-study eye) at the end of the 24-week treatment phase. In this study, the responder rate was significantly greater with teprotumumab treatment compared to placebo (69% versus 20%;  $p < 0.001$ ) at Week 24. Therapeutic effects were rapid, with increased responder rates in the teprotumumab group relative to placebo detected at Weeks 6, 12, and 18 (all  $p < 0.001$ ). The secondary endpoints (QoL, proptosis, and CAS as continuous variables) all supported the primary analysis conclusion that teprotumumab was superior to placebo in the treatment of TED. Population PK modeling in TED01RV confirmed that trough concentrations were consistently above the 20 µg/mL threshold, which had been previously determined by Roche PK/PD modeling as resulting in > 90% IGF-1R occupancy in the tissues. Results of the TED01RV study were published in the New England Journal of Medicine [Smith et al, 2017].

Of the AESIs identified in the oncology studies (i.e., infusion-associated events, thrombocytopenia, hyperglycemia, and anemia), the only one that emerged in the initial trial in subjects with TED was hyperglycemia. Among subjects treated with teprotumumab, hyperglycemia was uniformly mild in non-diabetic subjects and adequately controlled by

adjusting standard anti-diabetic therapy in diabetic subjects. Importantly, hyperglycemia in all teprotumumab-treated subjects was at Baseline levels after the end of the Treatment Period.

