#### 7.1.3.4.4 Pharmacodynamic Markers

#### 7.1.3.4.5 Safety

##### 7.1.3.4.5.1 River Vision TED01RV Study

Treatment-emergent AEs (TEAEs) in TED01RV that were reported for at least 5% of the subjects in the teprotumumab group and had a greater frequency than that in the placebo group are shown in [Table 7.2](#). The majority of AEs were mild, required no treatment, and resolved while subjects remained on drug. Hyperglycemia, which was monitored by assessing blood glucose and HbA1c, was the only AE clearly identified as related to study drug.

**Table 7.2 Summary of TEAEs Reported in at Least 5% of Subjects in Teprotumumab Treatment Group and % is Greater Than Placebo**

TEAEs	Placebo N=44 n (%)	Teprotumumab N=43 n (%)	Summary Details for TEAEs in Teprotumumab Group
Any TEAE	32 (72.7)	32 (74.4)	
Nausea	4 (9.1)	8 (18.6)	Generally mild and reported after first/second infusions
Muscle spasms	2 (4.5)	8 (18.6)	Intermittent, 2/8 cases experienced for >1 week and treated with muscle relaxants
Diarrhea	2 (4.5)	6 (14.0)	Treatment required in 2/6 cases, 1 designated an SAE (see below)
Hyperglycemia	2 (4.5)	5 (11.6)	Mechanism-based AE
Alopecia	2 (4.5)	3 (7.0)	All mild and no treatment required
Dry skin	0	3 (7.0)	All mild, one case used topical dry skin cream
Dysgeusia	0	3 (7.0)	For 2/3 cases a transient “metallic” taste on Days 1-2
Headache	2 (4.5)	3 (7.0)	Generally mild, one subject took paracetamol
Paresthesia	0	3 (7.0)	“Tingling” reported in nose, feet or chest; variable onset and in 2/3 cases occurred on 1 day
Hearing impaired	0	3 (7.0)	Disparate symptoms, onset and duration (i.e., one unilateral with onset 16 weeks after end of therapy, one mild bilateral that resolved, one intermittent in a subject with positive history of tinnitus)
Weight loss	0	3 (7.0)	Variable timing; decreases range from 5-9 lb.

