After completion of the Treatment Period, subjects who were proptosis non-responders in Study HZNP-TEP-301 will enter a 24-week Follow-Up Period, during which study drug will not be administered and clinic visits are scheduled for 1, 3, and 6 months (visit months 7, 9, and 12) after the Week 24 Visit; if any of these subjects discontinue from the Follow-Up Period prior to the Month 12 Visit, they will return to the clinic and undergo the scheduled Month 12 assessments prior to study discharge. Those who complete the Month 12 Visit will be contacted 6 and 12 months later via phone or email by research staff to enquire if any treatment for TED has been received since last study contact. If yes, subject will be questioned regarding type of treatment and outcome/response.

Subjects who relapsed during the Follow-Up Period of HZNP-TEP-301 and choose to enter this extension study will not participate in the Follow-Up Period. For these subjects, the last clinic visit is at Week 24. Those who complete the Week 24 Visit will be contacted 6 and 12 months later via phone or email by research staff to enquire if any treatment for TED has been received since last study contact. If yes, subject will be questioned regarding type of treatment and outcome/response.

[figure not shown]
An overview of the study design is presented in [Figure 9.1](#), and details of study activities were previously presented in [Section 2.1, Schedule of Assessments](#).

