## 9.2 Discussion of Study Design

The study population consists of subjects who participated in the lead-in study (HZNP-TEP-301) and who were either proptosis non-responders at Week 24 of HZNP-TEP-301 or were proptosis responders at Week 24 but meet the criteria for re-treatment due to relapse (see [Section 9.3.4](#)) during the Follow-Up Period of HZNP-TEP-301. The study population enrolled in HZNP-TEP-301 was well-defined and consistent with the expected target population for whom teprotumumab will be indicated (adult subjects with active moderate-to-severe TED).

The measurements used in this study for the primary and secondary endpoints (proptosis, CAS, and GO-QoL questionnaire) are established and well-validated endpoints that have been shown to correlate significantly with TED.

In order to maintain the study mask in HZNP-TEP-301, all subjects in this open-label extension study will undergo the same dosing regimen of teprotumumab (10 mg/kg on Day 1 followed by 20 mg/kg q3W for the remaining 7 infusions), regardless if they received teprotumumab or placebo in HZNP-TEP-301.

Given the teratogenic effects of teprotumumab noted in a monkey embryo-fetal development toxicity study (see [Section 7.1.3.2](#) for details) and PK profile of teprotumumab (see [Section 7.1.3.4.3](#)), all subjects (men and women) are required to use adequate contraception and report any pregnancies for at least 6 months after the last dose of study drug. Six months after the last dose, the estimated plasma concentration (0.2 µg/mL) is considered reasonably safe with a low risk of teratogenicity. Furthermore, a 6-month waiting period is in line with recommendations given for other teratogens, such as cytostatic chemotherapy.

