#### **9.5.4.1.5 Reporting and Documenting SAEs**

All SAEs beginning with the time of signing of the ICF and continuing until 30 days after study discharge must be reported. The following steps will be taken to report promptly and document accurately any SAE, whether or not it appears to be related to the study medication:

1. Report the SAE to the Sponsor **by entering the information in the eCRF within 24 hours** after becoming aware that a subject has experienced an SAE. If unable to access the eCRF, the event must be reported by submitting the completed SAE form by email to [REDACTED] fax, or telephone **within 24 hours** after becoming aware that a subject has experienced an SAE (see [Appendix 17.1](#) for contact information).
2. Perform appropriate diagnostic tests and therapeutic measures, and submit all follow-up substantiating data, such as diagnostic test reports, hospital discharge summaries, and autopsy report to the Sponsor's representative.
3. Respond in a timely manner to any queries from Sponsor regarding the SAE.
4. Conduct appropriate consultation and follow-up evaluation until the SAE is resolved, stabilized, or otherwise explained by the Investigator.
5. Review each SAE report and evaluate the relationship of the SAE to study treatment. The Sponsor will determine whether the SAE is unexpected in nature.
6. The Investigator must report all AEs or SAEs that meet the criteria for Unanticipated Problems Involving Risks to Human Subjects or Others to the IRB/IEC.

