##### **9.5.6.15.2 Month 18 – Follow-Up Contact for Subjects Who Relapsed in Study HZNP-TEP-301**

Subjects who complete the Week 24 Visit will be contacted 12 months later via phone or email by research staff to enquire if any treatment for TED has been received since last study contact. If yes, subject will be questioned regarding type of treatment and outcome/response.

This is the final contact for subjects who relapsed in Study HZNP-TEP-301.

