10.3.1. Adverse Events of Special Interest

Adverse events of special interest will be identified as follows:

- Potential infusion-related reactions: TEAEs that occur within 2 hours after initiating infusion
- Anaphylactic reactions: TEAEs that occur within 2 hours after initiating infusion and meet any one of the 3 criteria from Section 2.6.3 of the Introductory Guide for Standardised MedDRA Queries (SMQs) ([MedDRA, 2017](#)):
 - A narrow term or a term from Category A
 - A term from Category B AND a term from Category C
 - A term from Category D AND [a term from Category B OR a term from Category C]

- Hyperglycemia: TEAEs by any PTs under the SMQ “Hyperglycaemia/new onset diabetes mellitus” (narrow).
- Muscle spasm: TEAEs by the PT “muscle spasm”
- Diarrhea: TEAEs by any PTs under the SMQ “Noninfectious diarrhea” (broad search)
- Hearing loss: TEAEs by any PTs under the SMQ “Hearing impairment” (a sub-SMQ under “Hearing and vestibular disorders”) and HLT “Hearing losses”
- Potential infusion-related reactions of any type that are missing the onset time: TEAEs that are missing the AE start time, occur on the day of an infusion and meet one of the following criteria:
 - SMQ Angioedema (broad)
 - SMQ Hypersensitivity (broad)
 - SMQ Hypertension (narrow)
 - SMQ Anaphylactic reactions - meet any of the 3 criteria from Section 2.6.3 of the Introductory Guide for SMQs ([MedDRA, 2017](#)):
 - A narrow term or a term from Category A
 - A term from Category B AND a term from Category C
 - A term from Category D AND [a term from Category B OR a term from Category C]
 - HLTs: “Rashes, eruptions and exanthems NEC”, “Erythemas”, “Pruritus NEC”
 - PTs: Pyrexia, Flushing, Feeling hot, Chest pain, Chest discomfort, Myalgia, Myalgia intercostal, Back pain, Dizziness
- Potential infusion-related reactions excluding those of an anaphylactic nature that are missing the onset time: TEAEs that are missing the AE start time, occur on the day of an infusion and meet one of the following criteria:
 - SMQ Angioedema (broad)
 - SMQ Hypersensitivity (broad)
 - SMQ Hypertension (narrow)
 - HLTs: “Rashes, eruptions and exanthems NEC”, “Erythemas”, “Pruritus NEC”
 - PTs: Pyrexia, Flushing, Feeling hot, Chest pain, Chest discomfort, Myalgia, Myalgia intercostal, Back pain, Dizziness

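### Relapse subjects have no planned adverse-event enquiry after Week 24, about 21 days after the last dose, while lead-in non-responders are asked to about 189 days

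*Protocol*

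**What the plan says.** Protocol 9.1 states: "Subjects who relapsed during the Follow-Up Period of HZNP-TEP-301 and choose to enter this extension study will not participate in the Follow-Up Period". Their last clinic visit is Week 24. The contact that follows at Month 12 is made "to enquire if any treatment for TED has been received since last study contact", with questions on type of treatment and outcome if the answer is yes. Month 18 repeats this, and section 9.5.6.15.2 closes with: "This is the final contact for subjects who relapsed in Study HZNP-TEP-301". Both contacts are limited to subjects who complete the Week 24 visit.

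The AE/SAE row of the Schedule of Assessments (Protocol 2.1; SAP Table 1) is marked through Week 24 for everyone and through Month 12 for lead-in non-responders. It is blank in every contact column. Protocol 9.5.4.1.2 ends the treatment-emergent period 3 weeks after the last dose and collects later AEs through the end of the Follow-Up Period, which relapse subjects do not enter. Non-responders are asked about signs and symptoms at Months 7, 9 and 12 (9.5.6.12 to 9.5.6.14.1).

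Some duties do reach beyond Week 24:

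- SAEs (9.5.4.1.5): "All SAEs beginning with the time of signing of the ICF and continuing until 30 days after study discharge must be reported".
- An SAE that the investigator observes after study completion and believes possibly drug-caused is reportable, with no time limit (9.5.4.1.2).
- Ongoing drug-related AEs are followed to resolution or stabilisation (9.5.4.1.6).
- Pregnancies are reportable to 180 days after the last dose (9.5.4.2).

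**The concern.** Safety is part of the study's overall objective (Protocol 8), and late safety after retreatment is something that an extension study is well placed to describe. For relapse subjects, active enquiry stops one dosing interval after the last infusion. The two later contacts are already planned but carry no safety question.

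The protocol's own background suggests that this is early. On drug level, section 7.1.3.4.1 says: "Population PK modeling in TED01RV confirmed that trough concentrations were consistently above the" 20 µg/mL threshold, which it links to more than 90% receptor occupancy. Section 9.2 says: "Six months after the last dose, the estimated plasma concentration" is 0.2 µg/mL. On events, Table 7.2 describes three hearing events among 43 treated subjects in the earlier placebo-controlled TED study, "one unilateral with onset 16 weeks after end of therapy". The SAP then makes hearing loss an event of special interest (10.3.1: "Hearing loss: TEAEs by any PTs under the SMQ" for hearing impairment) and indexes a Follow-Up Period table of such events (14.3.1.7.3). A relapse subject with an event of similar timing would not be asked about it at any planned contact.

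At stake is the description of late events, non-serious ones above all, in subjects retreated after a relapse.

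**Working it through.** **Inputs.** Target days from SAP 6.4: Week 21 (last infusion) = 148, Week 24 = 169, Week 48/Month 12 = 337. Windows from the schedule: Week 21 ±3 days, Week 24 ±7, Month 12 contact for relapse subjects ±14. Infusions: 8 in this study and 8 in the lead-in (Protocol 7.2).

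**1. The plan's own 3 weeks.** 169 − 148 = 21 days, which agrees with the treatment-emergent period in 9.5.4.1.2.

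**2. Last planned AE enquiry, relapse subjects.** 21 days after the last dose. With windows, from (169 − 7) − (148 + 3) = 11 to (169 + 7) − (148 − 3) = 31 days.

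**3. Last planned AE enquiry, lead-in non-responders.** 337 − 148 = 189 days. The difference is 189 − 21 = 168 days.

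**4. Exposure.** Lead-in teprotumumab: 8 + 8 = 16 infusions, for non-responders and relapsers alike. Lead-in placebo: 0 + 8 = 8, again in both groups. The difference in follow-up therefore does not track exposure.

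**5. Drug level.** Above 20 µg/mL at trough against 0.2 µg/mL at six months: 20/0.2, so at least 100-fold higher. This assumes that the trough in the earlier study applies to a 3-week interval, as used here. Levels between the two points cannot be recovered because the pharmacokinetic section is blacked out; the point does not need them.

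**6. The SAE limit.** The current text does not define discharge for relapse subjects. Protocol 9.3.3 and SAP 7.1 treat Week 24 as completion, which gives 21 + 30 = 51 days after the last dose. If discharge is the Month 18 contact (Week 72, Day 72 × 7 + 1 = 505), the limit is (505 − 148) + 30 = 387 days. SAEs are then reportable for longer, but still nobody asks, and non-serious AEs stay outside.

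**7. The late hearing event.** 16 × 7 = 112 days if counted from the last dose; 112 + 21 = 133 if counted from a visit 3 weeks later. Either falls after day 21 and day 51 and before day 189. One in 43 is 2.3% (exact 95% interval 0.06% to 12.3%), which is compatible with a very rare event.

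**8. What the existing call would reach.** At target it falls on day 189; with its window, 189 ± 14 = 175 to 203; with the Week 21 window added, 172 to 206. Set against the 180-day pregnancy-reporting period, enquiry now reaches 21/180 = 11.7%. A question at the call would reach at least 175/180 = 97%, or 172/180 = 96% with both windows at their earliest.

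**The case against.** The strongest reply is that this is a deliberate and consistently stated design: the contacts serve to learn about TED treatment in both groups, and nothing in the documents contradicts itself. That is so. The point is an inexpensive improvement, not the correction of an error.

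It is also fair that passive provisions cover serious events and pregnancy. A reader might infer that there is no safety reporting after Week 24; that would be wrong. But each provision depends on someone volunteering or noticing the event.

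Four other stronger readings are tempting, and the documents do not support them:

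- *Relapse subjects have the highest exposure, so the study cannot describe late events after retreatment.* Non-responders given teprotumumab in the lead-in also reach 16 infusions, start within 14 days of lead-in Week 24, and are followed to Month 12.
- *The 180 days is a general risk period.* Sections 9.2 and 9.5.4.2 set it for contraception and pregnancy reporting, on teratogenicity grounds.
- *The hearing case shows a late drug effect.* It is one case, Table 7.2 calls the three cases disparate, and the note to Table 9.1 says that hearing loss is not considered causally associated. Hearing loss is not on the protocol's own list of events of special interest (9.5.4.1.1.5), only on the SAP's.
- *Planned safety comparisons are biased by enrolment type.* SAP 10.3 plans no AE table by enrolment type. Its Follow-Up denominator is subjects entering that period, which on its face leaves relapse subjects out, although the gloss in brackets is loose.

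**Conclusion.** The gap is real and limited. Planned AE enquiry ends about 21 days after the last dose for relapse subjects (11 to 31 with visit windows) and about 189 days after it for lead-in non-responders, at the same possible cumulative exposure. In the relapse subgroup, non-serious AEs after Week 24 go unasked, and SAEs and pregnancies are reportable but not enquired about.

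The day counts rest on SAP target days and a last infusion at Week 21. The judgement that 21 days is short rests on the documented contrast between more than 20 and 0.2 µg/mL and, weakly, on a single late hearing event; it does not rest on any modelled concentration. The documents give no number of relapse subjects, so the count of events that might be missed cannot be estimated.

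**What to change.** At the existing Month 12 contact for relapse subjects (Protocol 9.5.6.14.2), add a general, non-leading AE/SAE question and a question on whether a pregnancy has occurred. Extend the AE and SAE reporting periods in 9.5.4.1.2 and 9.5.4.1.5 to that contact for these subjects. This also removes the doubt about what discharge means for them up to that point.

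In the SAP, report these AEs apart from the clinic-collected Follow-Up Period AEs, labelled as collected by contact and with relapse subjects as their own denominator. Do not add a hearing-specific question for relapse subjects alone: non-responders are not prompted in that way, so it would create the unequal ascertainment that the change is meant to reduce.

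The cost is a call script, an eCRF page and amendment wording, with no new visit or call for subjects who complete Week 24. The drawback is that recall over about six months is less precise than collection at three clinic visits, which is why the events should not be pooled. A call made at the early edge of its window would miss the last 5 to 8 of the 180 days. Calling dosed relapse subjects who stopped early would be a new contact and is optional.
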